### **11.1.2 Unexpected Adverse Event**

An expected AE is one for which the nature or severity is consistent with the known AE profile of the product. For a pre-approval test product, the known information is contained in the IB. For a marketed product, the known information is contained in the current package insert for the product.

An unexpected adverse event (UAE) is one for which the nature or severity of which is not consistent with the applicable product information (e.g., IB for an unapproved investigational product or package insert/summary of product characteristics for an approved product). For example, hepatic necrosis would be unexpected (greater severity) if the IB only listed elevated hepatic enzymes or hepatitis. Likewise, cerebral thromboembolism and cerebral vasculitis would be unexpected (greater specificity) if the IB only listed cerebral vascular accidents.

Furthermore, reports that add significant information on specificity or severity of a known, already documented adverse reaction constitute unexpected events. Examples would be (a) acute renal failure as an expected adverse reaction with a subsequent new occurrence of interstitial nephritis (interstitial nephritis would be unexpected) and (b) hepatitis with a first occurrence of fulminant hepatitis (fulminant hepatitis would be unexpected.)

### **11.1.3 Serious Adverse Events**

A serious adverse event (SAE) is any untoward medical occurrence that at any dose:

- results in death
- is life-threatening

NOTE: The term “life-threatening” in the definition of “serious” refers to an event in which the subject was at risk of death at the time of the event; it does not refer to an event that hypothetically might have caused death if it were more severe.

- requires inpatient hospitalization or prolongation of existing hospitalization

An elective hospital admission to treat a condition present before exposure to the IP, or a hospital admission for a diagnostic evaluation of an AE, does not qualify the condition or event as an SAE

- results in persistent or significant disability/incapacity

- is a congenital anomaly

NOTE: A congenital anomaly in an infant born to a mother who was exposed to the IP during pregnancy is an SAE. However, a newly diagnosed pregnancy in a subject that has received an IP is not considered an SAE unless it is suspected that the IP(s) interacted with a contraceptive method and led to the pregnancy.

- is an important medical event

NOTE: Medical and scientific judgment should be exercised in deciding whether it is appropriate to consider other situations serious, such as important medical events that may not be immediately life-threatening or result in death or hospitalization but may jeopardize the subject or may require intervention to prevent one of the other outcomes listed in the definition above. Examples of such events are intensive treatment in an emergency room or at home for allergic bronchospasm, blood dyscrasias, or convulsions that do not result in hospitalization, development of drug dependency, or drug abuse.

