### 11.1. Definitions

#### 11.1.1 Adverse Events

An AE is defined as any untoward medical occurrence in a patient or clinical investigation subject administered a pharmaceutical product that does not necessarily have a causal relationship with this treatment. An AE can therefore be any unfavorable and unintended sign (including an abnormal laboratory finding, for example), symptom, or disease temporally associated with the use of a medicinal product, whether or not related to the medicinal product.

Pre-existing diseases or conditions will not be considered AEs unless there is an increase in the frequency or severity, or a change in the quality, of the disease or condition. (Worsening of a preexisting condition is considered an AE.) A pre-existing condition is one that is present at the start of the study. A pre-existing condition should be recorded as an AE if the frequency, intensity, or the character of the condition worsens during the study period (after signing the ICF up to Visit 14 and Visit 15/Follow-up).

For subjects who enter the present study within 14 days of their antecedent PH94B SAD study, AEs ongoing at the time of enrollment into the present study will be recorded in the medical history section of the present study.

Abnormal results of diagnostic procedures are considered to be AEs if the abnormality:

- results in study withdrawal and is associated with an SAE
- is associated with clinical signs or symptoms
- leads to additional treatment or to further diagnostic tests
- is considered by the Investigator to be of clinical significance

In addition, a clinical laboratory abnormality must be documented as an AE if any 1 of the following conditions is met:

- The laboratory abnormality is not otherwise refuted by a repeat test to confirm the abnormality
- The abnormality suggests a disease and/or organ toxicity
- The abnormality is of a degree that requires active management, e.g., change of dose, discontinuation of the drug, more frequent follow-up assessments, further diagnostic investigation, etc.

Pregnancy is not considered an AE, but it is an important medical event, which must be followed up as described in Section 11.3.1.

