### **11.2.6 Reporting**

#### **11.2.6.1 Serious Adverse Events**

The Investigator or designee must report all SAEs promptly to [REDACTED] within 24 hours of first becoming aware of the event by completing, signing, and dating the Serious Adverse Event Report Form, verifying the accuracy of the information recorded in the form with the source documents and eCRF, and sending the SAE Report Form to [REDACTED] by one of the following methods:

email: [REDACTED]

Fax number (back-up): [REDACTED]

This written report should be submitted on the SAE form provided for this purpose. At the time of first notification, the Investigator or designee should provide the following information, if available:

- Protocol number
- Reporter (study site and Investigator)
- Subject's study number
- Subject's date of birth
- Subject's gender
- Date of first dose of IP
- Date of last dose of IP, if applicable
- Adverse event term
- Date of occurrence of the event
- A brief description of the event, outcome to date, and any actions taken
- The seriousness criteria(on) that were met
- Concomitant medication at onset of the event
- Relevant medical history information

- Relevant laboratory test findings
- Investigator's opinion of the relationship to IP ("Is there a reasonable possibility that the IP caused the SAE? Yes or No?")
- Whether and when the Investigator was unblinded as to the subject's treatment assignment

Any missing or additional relevant follow-up information concerning the SAE should be sent to the sponsor/sponsor representative via the same contact details above as soon as possible, and within 7 days, on a follow-up SAE Report Form, together with the following minimal information (initial report, AE, date of occurrence, subject identification [ID], study ID, IP, and site number); this will allow the follow-up information to be linked to the initial SAE report.

Specific information may be requested by the [REDACTED] Pharmacovigilance Department using a follow-up request form sent via email communication.

The Investigator is required to comply with applicable regulations (including local laws and guidances) regarding the notification of his or her health authorities, IRB, principal and coordinating investigators, study investigators, and institutions. Each investigator is obligated to learn about the reporting requirements for investigators in his/her country. The study monitor may be able to assist with this.

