## **11.3. Special Considerations**

### **11.3.1 Pregnancy**

All women of childbearing potential who participate in the study should be counseled on the need to practice adequate birth control and on the importance of avoiding pregnancy during study participation. Women should be instructed to contact the investigator or study staff immediately if pregnancy occurs or is suspected.

Pregnancy testing will be conducted prior to administration of the IP on every woman of childbearing potential. A woman who is found to be pregnant at the Screening visit will be excluded from the study and considered to be a screening failure.

A woman who becomes pregnant during IP treatment or within 14 days of discontinuing the IP will be immediately discontinued from study participation. The Investigator must report the pregnancy within 48 hours of learning of the pregnancy, to [REDACTED] Pharmacovigilance using the Pregnancy Data Collection Form via the same fax number and/or email address as for SAE reporting (see Section 11.2.6.1). The Investigator should contact the designated individual(s) who receive SAE notification and record information related to the pregnancy on an Exposure in Utero form provided by the sponsor or its designee.

Early Termination Visit assessments are required as soon as possible after learning of the pregnancy. The Investigator is also responsible for following the pregnancy until delivery or termination. These findings must be reported on the Exposure in Utero form and forwarded to the

designated individual(s). The event meets the SAE criterion only if it results in a spontaneous abortion or a congenital anomaly.

Male subjects with partners of childbearing potential should be advised to use contraception throughout their participation in the study. If the partner of a male subject becomes pregnant during his IP treatment or within 14 days of his discontinuing the IP, the Investigator must report the pregnancy within 48 hours of learning of the pregnancy, to [REDACTED] Pharmacovigilance, as described above.

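### The SAE definition exempts admissions for diagnostic work-up of an AE without limiting them to elective stays, and the pregnancy sections conflict on what is an SAE, so some events may not be classed as SAEs or reported within 24 hours

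*Protocol*

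**What the plan says.** **Hospitalization.** Protocol Section 11.1.3 lists among the SAE criteria an event that "requires inpatient hospitalization or prolongation of existing hospitalization". The text directly under that bullet takes out two kinds of admission. The first is an elective admission to treat a condition that predates exposure to the product. The second is the limb "or a hospital admission for a diagnostic evaluation of an AE, does not qualify the condition or event as an SAE". Urgency, AE severity and length of stay are not mentioned in the second limb.

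**Important medical events.** The same section keeps a judgment-based route for other situations, "such as important medical events that may not be immediately life-threatening or result in death or hospitalization but may jeopardize the subject".

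**Pregnancy.** Three sections speak to it:
- Section 11.1.1: "Pregnancy is not considered an AE, but it is an important medical event".
- Section 11.1.3, in the note on congenital anomaly: a new pregnancy "is not considered an SAE unless it is suspected that the IP(s) interacted with a contraceptive method and led to the pregnancy".
- Section 11.3.1: "The event meets the SAE criterion only if it results in a spontaneous abortion or a congenital anomaly".

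**Clocks.** Section 11.2.6.1 requires SAEs to be reported "within 24 hours of first becoming aware of the event". Section 11.3.1 says: "The Investigator must report the pregnancy within 48 hours of learning of the pregnancy".

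**Which section decides.** Section 11.2.2.2 refers the seriousness decision to Section 11.1.3 and does not mention Section 11.3.1. SAP Section 8.1.2 tabulates serious TEAEs but gives no seriousness or pregnancy rule of its own.

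**The concern.** SAE incidence is part of the first-listed safety endpoint (Protocol Section 13.1.4) in a single-arm study whose sample size was chosen to build a safety database (Section 13.2). Section 12 states that there is no data safety monitoring board. Section 11 describes medical monitoring as including periodic review of how many SAEs occur and of what type. The interim safety analysis in Protocol Section 13.1.6 was dropped (SAP Sections 4.2 and 10). The serious/nonserious label therefore matters both for the final tables and for what is seen quickly during the study.

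Hospitalization is normally the objective trigger in an SAE definition: the subject was admitted or was not. Many unplanned admissions begin as evaluation, for example of chest pain, syncope or a change in mental state. If the purpose of the admission can remove it from the criterion, two sites can label the same admission differently, and each can point to the text. The pregnancy sections create the same problem by a different route, since the label depends on which section the site opens.

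**Working it through.** The plan gives no figure to reproduce, so the main check is a comparison of the rules.

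**Step 1. Scope of the diagnostic limb.** In Section 11.1.3, elective and the reference to a condition present before exposure belong to the first limb. The second limb is defined by its purpose, evaluation of an AE, and so by its terms reaches events that are new on treatment. It sits under the hospitalization bullet, so the criteria for death, life-threatening events, disability, congenital anomaly and important medical events remain. The section also gives emergency-room treatment of convulsions without admission as an example of a serious event, while an actual admission for evaluation is exempt from the hospitalization route.

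**Step 2. Classification of four cases.**

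| Case | Section 11.1.3 | Section 11.3.1 |
|---|---|---|
| Unplanned admission solely to evaluate a new AE | Not an SAE through hospitalization; SAE only if another criterion is judged to apply | Not addressed |
| Pregnancy with suspected product-contraceptive interaction | SAE | Not an SAE |
| Spontaneous abortion | Not named; SAE only through another criterion | SAE |
| Congenital anomaly | SAE | SAE |

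The two sections agree only on congenital anomaly. Each is broader than the other on one of the remaining pregnancy cases.

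**Step 3. Does another section settle it?** Section 11.1.1 does not: it calls pregnancy an important medical event, which is the name of an SAE criterion in 11.1.3, while saying that it is not an AE. Section 11.2.2.2 points to 11.1.3 alone, which would leave the 11.3.1 sentence without effect. The SAP is silent.

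**Step 4. Clocks.** For a pregnancy with suspected contraceptive interaction, a site following 11.1.3 has 24 hours and a site following 11.3.1 has 48 hours. The difference is 48 − 24 = 24 hours, plus a possible missing SAE flag.

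**Step 5. Scale.** No admission, pregnancy or SAE rate is given, so the number of affected events cannot be derived. What can be shown is the leverage of each event, using assumed counts x among n treated subjects and exact (Clopper-Pearson) two-sided 95% limits. The protocol's 600 is a ceiling, so smaller n are shown as a range.

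- Shift per subject: 1/n, so 1/600 = 0.17, 1/300 = 0.33 and 1/100 = 1.0 percentage points.
- n = 600: 0 events, upper limit 0.61%; 1 event, 0.17% (0.004% to 0.93%); 3 events, 0.50% (0.10% to 1.45%).
- 1 event at n = 300: upper limit 1.84%. At n = 100: upper limit 5.45%.

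These figures show sensitivity only. They do not estimate how many events would be reclassified.

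**The case against.** The strongest reply is that the diagnostic limb is part of the hospitalization criterion. An exempted admission does not satisfy the protocol's definition and then go missing; the definition is simply broad. That stands. Part one concerns the width of an exemption, whereas only the pregnancy part is a conflict between rules.

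The other SAE routes also remain open, and a convulsion or an event that endangers the subject can be serious without any admission. This stands too, but the important-medical-event route rests on investigator judgment, so it does not restore an objective trigger.

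Four stronger readings are tempting, and the documents do not support them:
- **That the events go uncounted.** Section 11.2 has all AEs not meeting SAE criteria entered on the eCRF, Section 11.2.3 records seriousness including hospitalization, and Section 10.2.2.1 tells subjects to phone the site about hospitalizations. What may be lost is the SAE label and the fast report.
- **That the bias runs only toward fewer SAEs.** The diagnostic limb can only lower the count. For pregnancy the direction is not fixed, because 11.3.1 is broader than 11.1.3 on spontaneous abortion.
- **That the restriction in 11.3.1 shuts out maternal death or a life-threatening complication.** The sentence most naturally refers to the pregnancy itself. A complication is its own untoward event, to be judged under 11.1.3.
- **That a number of lost SAEs can be stated.** Any such number needs an assumed admission rate and an assumed share labelled diagnostic, and neither is in the documents. Comparing the result with 0 of 600 would be wrong as well, since such assumptions normally leave other admissions still counted as SAEs.

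It is also fair to say that the two clocks attach to different forms and can both run, and that the 48-hour pregnancy report goes through the same contact route as SAE reports. This limits the practical harm but does not resolve which label applies.

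**Conclusion.** The point holds in two parts. First, the diagnostic-evaluation limb in Section 11.1.3 has no limit by urgency, so an unplanned admission to evaluate a new AE may be left out of the SAE counts and the 24-hour report unless another criterion is judged to apply. Second, Sections 11.1.1, 11.1.3 and 11.3.1 cannot all be followed on pregnancy, and the conflict runs in both directions, with different reporting clocks attached.

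The consequence is a risk of inconsistent classification between sites; a loss of events is not established. The overall size is unknown. With a single-arm, descriptive analysis and no formal safety testing (SAP Section 8), no hypothesis test is affected, but the SAE component of the primary safety endpoint is. Severity: should be fixed. The conclusion rests on the wording alone. A safety management plan or SAE form guide outside these documents might narrow the exemption in practice.

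**What to change.** 1. **Section 11.1.3, hospitalization.** Delete the diagnostic-evaluation limb, or limit it to elective, pre-planned admissions, so that an unplanned inpatient admission for an AE counts under the hospitalization criterion.
2. **Sections 11.1.1, 11.1.3 and 11.3.1, pregnancy.** Reconcile them into one seriousness rule. In 11.3.1, replace the restrictive sentence with a cross-reference to all criteria in 11.1.3. In 11.1.3, state explicitly how spontaneous abortion and suspected contraceptive interaction are classed. Bring the description of pregnancy in 11.1.1 into line.
3. **Clocks.** State that any pregnancy event classed as an SAE is reported within 24 hours, and that other pregnancies stay on the 48-hour form.

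The cost is a few sentences in the protocol and the matching lines in the SAE form guidance, a few more SAE reports, and a slightly higher reported SAE rate.

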#### **11.1.4 Significant Adverse Events**

Other significant AEs are defined as marked hematological and other laboratory abnormalities (other than those meeting the definition of serious) and any events that led to an intervention, including withdrawal of test drug, dose reduction, or significant additional concomitant therapy.

#### **11.1.5 Treatment-emergent Adverse Events**

Treatment-emergent AEs are defined as:

- AEs with onset at the time of or following the start of treatment with IP through the Follow-up Visit, or
- AEs starting prior to the start of treatment but increasing in severity or relationship at the time of, or following, the start of treatment with IP through the Follow-up Visit

### **11.2. Event Assessment and Follow-up of Adverse Events**

The Investigator will record all reportable events with start dates occurring any time after informed consent is obtained until 14 days after the last day of study participation. At each study visit, the Investigator will inquire about the occurrence of AE/SAEs since the last visit. Events will be followed for outcome information until resolution or stabilization.

The occurrence of an AE or SAE may come to the attention of study personnel during study visits and interviews of a study subject presenting for medical care, or upon review by a study monitor.

All AEs including local and systemic reactions not meeting the criteria for SAEs will be captured on the appropriate eCRF. Information to be collected includes event description, time of onset, clinician's assessment of severity, relationship to study product (assessed only by those with the training and authority to make a diagnosis), and time of resolution/stabilization of the event. All AEs occurring while on study must be documented appropriately regardless of relationship. All AEs will be followed to adequate resolution.

Any medical condition that is present at the time that the subject is screened will be considered as baseline and not reported as an AE. However, if the study subject's condition deteriorates at any time during the study, it will be recorded as an AE.

Changes in the severity of an AE will be documented to allow an assessment of the duration of the event at each level of severity to be performed. Adverse events characterized as intermittent require documentation of onset and duration of each episode.

#### **11.2.1 Assessment**

The Investigator is responsible for the detection and documentation of events meeting the criteria and definition of an AE or SAE described previously. At each visit, the subject will be allowed time to spontaneously report any issues since the last visit or evaluation. The Investigator will then monitor and/or ask about or evaluate AEs using nonleading questions, such as

- “How are you feeling?”
- “Have you experienced any issues since your last visit?”
- “Have you taken any new medications since your last visit?”

Any clinically relevant observations made during the visit will also be considered AEs.

In addition, the Investigator will review the eDiary summary text for health problems and determine whether they are to be recorded in the EDC system as AEs.

## 11.2.2 Evaluation

### 11.2.2.1 Severity of Adverse Events

The clinical severity of an AE will be classified as:

Mild	An event that is easily tolerated by the subject, causing minimal discomfort and not interfering with everyday activities
Moderate	An event that is sufficiently discomforting to the extent of interfering with normal everyday activities
Severe	An event that prevents the subject from performing normal everyday activities

It is important to distinguish between severe AEs and SAEs. Severity is a classification of intensity whereas an SAE is an AE that meets serious criteria, as described in Section [11.1.3](#).

### 11.2.2.2 Seriousness

The Investigator is to evaluate whether the AE meets serious criteria, as described in Section [11.1.3](#).

### 11.2.2.3 Actions Taken

Actions taken may consist of:

Dose not changed	An indication that a medication schedule was maintained.
Drug withdrawn	An indication that a medication schedule was modified through termination of a prescribed regimen of medication.
Not applicable	Determination of a value is not relevant in the current context.
Unknown	Not known, not observed, not recorded, or refused.

### 11.2.2.4 Outcome at the Time of Last Observation

The outcome at the time of last observation will be classified as:

- Recovered/resolved
- Recovered/resolved with sequelae
- Recovering/resolving
- Not recovered/not resolved

- Fatal\*
- Unknown

\*Investigators should only select fatal as an outcome when the AE results in death. If more than one AE is judged to be possibly related to the subject's death, the outcome of death should be indicated for each such AE. Although "fatal" is usually an event outcome, events such as sudden death or unexplained death should be reported as SAEs.

